7.4.4 Reporting to ethical committees and regulatory authorities

SAEs/SADEs/USADEs and device deficiencies that could have led to a SAE should be reported to ethics committees/institutional review board in accordance with local requirements.

7.5 Concomitant medication and treatments

All medications and treatments given, whether or not to treat AEs/ADEs, must be recorded in the appropriate section of the case report form.

8 Risk and benefits of the investigational device(s) and the clinical investigation

8.1 Anticipated clinical benefits

The Cochlear™ Baha® BA400 Abutment has been designed to remove the need to perform soft tissue reduction, to reduce skin complications and to improve the cosmetic outcome of the surgery. The surgical procedure will also be simplified.

8.2 Anticipated adverse device effects

The adjustment in the design of the new abutment is minimal from a risk perspective. Nevertheless the following risk with the new abutment BA400 in comparison with the current abutments BA300, has been hypothesised:

- Trauma
A longer abutment (BA400: 10 mm and 12 mm abutments) could increase the risk for trauma in comparison with shorter abutments (BA300 6 mm/9 mm and Baha snap coupling 8.5 mm).

In order to evaluate if longer abutments increase the risk of implant failure a comparison has been made between currently available abutments when it comes to reported implant failures in the Cochlear Complaint Management System (CREM) in relation to with the number of sold products.

The conclusion of the events reported in CREM is that there is no indication of an increased risk of implant failures with the 9 mm abutment compared to the 6 mm abutment

Product	Description	Number of sold products	Number of implant failures
92127 BIA300	Implant 4 mm with abutment 6 mm	11 600	21
92346 BIA300	Implant 4 mm with abutment 9 mm	1 800	4

A similar conclusion was drawn based on the literature search of Baha literature. Of the 55 articles selected for the clinical evaluation four (4) articles covered the use of the 8.5 mm long abutments. No implant failures were reported in these studies.

In conclusion, there exist no anticipated additional adverse device effect in comparison with the current abutment (BA300).

8.3 Residual risks associated with the investigational device

Clinical outcomes related to the use of Baha implants and abutments have been frequently reported in the scientific literature during the last decades. A literature review¹⁷ was performed in June 2012 in order to assess the current status of Baha implants and surgical products in terms of safety and efficacy. Fifty-five (55) scientific articles met the predefined review criteria. Only one (1) randomised controlled prospective study and one (1) non-randomised prospective study were encountered; the remaining studies were retrospective studies or case reports. One systematic literature review was also included. Ten (10) studies included only paediatric patients, while the remaining studies included

both paediatric and adult patients or adults only. Nineteen (19) of the studies included 100 or more patients.

Overall good outcomes, with acceptable implant survival rates and low incidence of significant adverse reactions, are reported. However, as with any surgical procedure, the use of Baha implants and surgical procedures is not free from complications, which is also reflected in the literature. Reported complications with Baha implants and surgical products are summarised at continuation.

Implant loss is a known complication with Baha implants, and can occur at any time point following implantation. Known reasons for implant loss include: primary failure of osseointegration, loss of osseointegration, trauma, infection leading to implant loss. The literature reports of cumulative implant survival rates in the range 73 to 100%, with the majority of authors reporting survival rates of 90% or higher.

Local skin reactions around the Baha abutment, ranging from slight redness to infected tissue, are the most common complications with Baha implants. Reports suggest that as many as 30% of the patients experience some kind of skin reaction at some point in time. However, the vast majority of skin complications are regarded as minor. Holgers grades of 0-1 are reported in 90-95% of observations, with adverse reactions (grade 2-4) only being reported in a few percent of observations

Excessive skin thickening or skin overgrowing the abutment is another relatively common soft tissue complication. The reported rate of skin thickening/overgrowth ranges between 0 and 22%. In cases where skin thickening recurs following localised treatment and skin revision surgery.

Incomplete or complete flap breakdown is another known complication with Baha implantation; this complication is generally not regarded as major.

Persistent pain at the implant site requiring removal of the implant has been reported by some authors and numbness in the area around the implant site has been reported in one study

8.4 Risks associated with participation in the clinical investigation

The test abutment, the control abutment and associated surgical procedures are CE marked and the procedures in this CIP are in accordance with the intended use.

8.5 Steps that will be taken to control or mitigate the risks

The surgical procedures associated with BA300 and BA400 are described in the Surgery Guides.

8.6 Risk-to-benefit assessment

After thorough analysis no foreseeable additional risks can be ascribed to the new abutment. Therefore the risks/adverse events are minimal and acceptable when weighed against the benefits of the intended performance of the investigational device/ comparator.

9 Statistical consideration

9.1 Statistical Design and Hypotheses considerations

9.1.1 Primary statistical aims

This study is designed as a superiority study with two primary statistical aims

1. To demonstrate that the combined endpoint of infection/inflammation, overgrowth, pain and numbness will be significantly lower in the group with the minimally invasive surgical procedure in combination with the use of the BA400 abutment compared to the traditional surgical procedure and abutment BA300.
2. To demonstrate that the minimally invasive surgical procedure in combination with the use of the BA400 abutment is associated with a significant reduction in direct medical costs, due to shorter surgical procedures, faster wound healing and less complications compared to the traditional surgical procedure in combination with the use of the standard BA300 abutment.

9.1.2 Secondary statistical aims

The secondary statistical aims are to show that the minimally invasive surgical procedure in combination with the use of the BA400 abutment is associated with a significant:

- reduction in infections/inflammations evaluated by Holgers Index
- reduction in soft Thickening/overgrowth scale
- reduction in time for wound healing will be evaluated as number of dressings
- reduction in numbness
- reduction in pain in the scar area and neuropathic pain
- reduction in surgery time
- improvement in the aesthetics

9.2 Sample size calculation

Sample size calculations are performed for both primary analyses. The significance level of 0.05 will be split between the two primary analyses: combined endpoint 0.0499 and direct medical cost 0.0001.

9.2.1 Sample size calculation for the combined endpoint of infection/inflammation, overgrowth, pain and numbness

For a definition of first primary endpoint, see section 5.2.1. It is estimated that the distribution of the number of events regarding infection/inflammation, overgrowth, pain and numbness with the traditional surgical procedure and BA300 abutment is as follows; 60% no events, 18% one event, 12% two events, 7% three events and 3% four events. In order to achieve a power of 80% with the Mantel-Haenszel two-sided chi-square test at significance level of 0.0499 when the distribution of the number of events with the new surgical procedure and new abutment BA400 is as follows; 81% no events, 13% one event, 5% two events, 1% three events and 0% four events we need 50 statistical evaluable subjects in each group. The sample size calculation is based on 10000 simulated studies.

9.2.2 Sample size calculation for direct medical costs, based on time for surgical procedures, wound healing and complications

For a definition of the second primary endpoint see section 5.2.1. The power that is achieved if the previously needed 50 statistical subjects in each group are used for the economic evaluation is calculated as follows, From a 12 months prospective follow-up by Hultcrantz² the mean time required for surgery was 44.57 (SD 7.41) minutes with skin reduction and 28.14 (SD 3.67) minutes without skin reduction. If a normal distribution of the costs time required for surgery, 15% infections/inflammations, 15% extra dressings with skin reduction, 9% infections/inflammations and 10% extra dressings without skin reduction, with a power of more than 99% with the two-sided Mann-Whitney U-test at a significance level 0.0001 would be achieved. The sample size calculation is based on 10000 simulated studies.

In order to compensate for a drop-out rate of 5% we need to randomize 53 subjects to each group

9.3 Analysis sets – populations

The Intention to Treat population (ITT) consists of all randomised patients with at least one follow-up measurement.

The per protocol population (PP) will include subjects that have completed the investigation according to the protocol. Subjects that were incorrectly randomised or were considered major protocol violators should be removed from the PP population.

The safety population consists of all surgical treated patients, grouped after surgical procedure.

The definition of the analyse sets (ITT, PP and Safety) will be taken at the clean file meeting before the database lock.

9.4 General statistical methodology

For comparison between the two study groups the Mantel-Haenszel chi-square test will be used for ordered categorical variables, the Mann-Whitney U-test for continuous variables, Fisher's exact test for dichotomous variables and the Chi-square test for non-ordered categorical variables.

The distribution of continuous variables will be given as n, mean, SD, Median, Min and Max and the distribution of dichotomous and categorical variables will be given as number and percentages.

The main analyses will be performed on the ITT population and complementary analyses will be performed on the PP population.

The main analyses will be performed unadjusted. If significant statistical differences in demographics and baseline variables are found, complementary analyses will be performed adjusted for these variables.

The main analysis will be after 12 months of follow-up and repeated after 3 years. All statistical tests will be two-sided.

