4.3 Randomisation

Subjects will be randomised to either:

- **Test group:** Minimally invasive surgery and the use of Cochlear Baha BA400 Abutment (investigational device).
- or
- **Control group:** Traditional surgery and the use of Cochlear Baha BA300 Abutment (comparator).

Randomisation will be performed in a proportion 1:1 ratio (test group/control group) at visit 2, i.e. the day of surgery, stratified for site with unknown block size.

Randomisation will be based on optimal allocation using a Web-based application.

If a subject discontinues participation in the investigation (see Section 'Discontinuation') his/her randomisation code/subject number will not be re-used. Discontinued subjects are not allowed to re-enter into the investigation.

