9.5 Efficacy analysis

9.5.1 Primary efficacy analyses

9.5.1.1 First primary analysis: combined endpoint of infection/inflammation, overgrowth, pain and numbness

The primary analysis of the number of events regarding infection/inflammation, overgrowth, pain and numbness (see definition section 5.2.1) between the two study groups will be analysed with the Mantel-Haenszel two-sided chi-square test at a significance level of 0.0499 on the ITT population between 3 weeks and 1 year.

9.5.1.2 Secondary primary analyses: direct medical costs, based on time for surgical procedures, wound healing and complications

The primary analysis of direct medical costs, based on time for surgical procedures, wound healing and complications (see definition section 5.2.1) between the two study groups will be analysed with two-sided Mann-Whitney U-test at significance level 0.0001 on the ITT population up to one year of follow-up.

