5.4 Demographics and Baseline Characteristics

Demographics and baseline characteristics will be summarised by treatment group for the ITT and PP populations. Continuous variables will be tested with Mann-Whitney U-test between the two groups, dichotomous variables with Fishers exact test, ordered categorical variables with Mantel-Haenszel Chi-square test and non-ordered categorical variables with Chi-square test. Site and country will not be tested between treatments.

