5.7 Efficacy Analyses

5.7.1 Primary Efficacy Analysis

5.7.1.1. Clinical analysis

The combined primary variable will be analysed by the Mantel-Haenszel Chi-square test. The variable will be summarised in a table as a categorical variable. A stacked bar chart (up to

STATISTISKA KONSULTGRUPPEN		Statistical Analysis Plan	
Protocol: Clinical and health economic evaluation with a new Baha abutment design combined with a minimally invasive surgical technique		Protocol No: CBAS5439	
		Version: 1.0	Page 17 of 23

100%) with one bar per treatment group will be produced. A plot of individual values of Holgers Index, Overgrowth, Pain (scar/neuropathic) according to POSAS or pain questions in CRF and Numbness with patient number on the y-axis and time (3 weeks to 1 year) on x-axis. The individual values will be shown as different symbols at each visit to indicate level of complication.

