5.7.2 Secondary Efficacy Analyses

The combined variable used in the primary analysis will also be analysed in the same way but for PP population and also only for subjects who completed all visits in the study.

The distribution of Holgers Index will be tested between treatment groups with Mantel-Haenszel Chi-square test at each visit. Holgers index by visit will also be presented in a figure. Max of Holgers Index per patient will be tested in the same way but only once and not per visit. The distribution of all Holgers Index values over all visits will be presented but no testing of this will be done.

Holgers Index according to AE reporting will be analysed by:

- Plot the incidence rate Holgers ≥ 2 per day over time
- Plot individual patient Holgers Index values using boxes/bars indicated by different colours by severity with patients on y-axis and calendar time on x-axis.
- The distribution of all Holgers Index values over all AEs will be presented by treatment group but no testing of this will be done.
- Plot visit Holgers data and movement between visits by treatment group.

The distribution of soft tissue thickening/overgrowth will be tested between treatment groups with Mantel-Haenszel Chi-square test at each visit.

The number of resources and costs of the components Direct medical costs will be summarised by treatment groups. The costs of the 3 components: surgery, wound dressing and complications will be tested between groups by using Mann-Whitney U test.

Wound healing will be tested between treatment groups by visit with Fishers exact test.

The visible abutment length and change from visit 3 will be tested between groups by visit by using Mann-Whitney U test. This test will only be done for patients with no change of abutment. For patients with an abutment change spaghetti plots will be created of the visual abutment length over time with indication of when abutment change is made and an indication of length of the new abutment.

The aesthetic outcome (POSAS) scales and the two pain questions will be tested between groups by visit by using Mann-Whitney U test.

The distribution of numbness will be tested between treatment groups with Mantel-Haenszel Chi-square test at each visit.

Surgery time will be tested between groups by using Mann-Whitney U test.

STATISTISKA KONSULTGRUPPEN		Statistical Analysis Plan	

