5.7.4.10. Smoking

Smoking habits (No, Smoking - Less than 10 cigarettes/day, Smoking - Between 11 and 20 cigarettes/day, Smoking - Between 21 and 40 cigarettes/day, Smoking - More than 40 cigarettes/day) at visits 1, 4, 6, 8, 9 and 10. For hypothesis generating purposes, a mixed model will be created using the primary outcome and smoking as measured during this study in the first year.

STATISTISKA KONSULTGRUPPEN		Statistical Analysis Plan	
Protocol: Clinical and health economic evaluation with a new Baha abutment design combined with a minimally invasive surgical technique		Protocol No: CBAS5439	
		Version: 1.0	Page 20 of 23

5.7.4.11. *Per site analyses*

Any previous specified analyses may be performed per site.

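### Randomisation is stratified by site but the primary clinical test pools all sites; if outcomes differ by site, the test is conservative and forgoes power (about 1 point at an assumed site variance share of 0.10)

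*Protocol*

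**What the plan says.** Protocol 4.3 randomises 1:1, "stratified for site with unknown block size". Site is the only stratification factor stated.

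The analysis does not carry that factor forward. Protocol 9.4 says "The main analyses will be performed unadjusted". Under protocol 9.5.1.1 the number of events "will be analysed with the Mantel-Haenszel two-sided chi-square test at a significance level of 0.0499 on the ITT population", and SAP 5.7.1.1 says "The combined primary variable will be analysed by the Mantel-Haenszel Chi-square test". Neither names a stratum. The test's name does not imply one here: protocol 9.4 lists it as the general two-group test for ordered categories, and SAP 5.4 uses it for baseline comparisons.

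Site does not enter by another route:

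- **Repeat analyses (SAP 5.7.2).** "The combined variable used in the primary analysis will also be analysed in the same way but for PP population", and likewise for subjects who completed all visits.
- **Adjusted complementary analyses (protocol 9.4).** These are run only for baseline variables that differ significantly between arms. SAP 5.4 says "Site and country will not be tested between treatments".
- **Per-site analyses (SAP 5.7.4.11).** These are optional: "Any previous specified analyses may be performed per site".
- **By-site presentation (SAP 5.7.3).** This belongs to the cost-consequence analysis.

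SAP section 7 records no change on this point.

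**The concern.** When arms are balanced within each site, differences between sites largely cancel out of the treatment contrast. A pooled test still counts those differences in its variance estimate, so it overstates the standard error. Its true type I error then falls below 0.0499, and it gives up power that a test using the randomisation stratum would keep.

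Some site variation is plausible. The trial is international, multicentre and open. Skin-care instruction follows local practice (protocol 6.3). The overgrowth scale was developed for this trial (protocol 7.3.2), and site staff explain the neuropathic pain item to patients (protocol 7.3.7). The documents do not say how much the combined endpoint varies by site.

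What is at stake is efficiency in a trial sized at its 80% target, with no replacement of subjects who discontinue (protocol 4.5).

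**Working it through.** **Inputs from protocol 9.2.1.** Event counts 0 to 4 are distributed 60/18/12/7/3% in control and 81/13/5/1/0% in test, with 50 evaluable subjects per group and two-sided alpha 0.0499.

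- Control mean: 0.18 + 0.24 + 0.21 + 0.12 = 0.75. Variance: 1.77 − 0.75² = 1.2075.
- Test mean: 0.13 + 0.10 + 0.03 = 0.26. Variance: 0.42 − 0.26² = 0.3524.
- Difference d = 0.49.

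**The plan's own figure.** The plan says "In order to achieve a power of 80% with the Mantel-Haenszel two-sided chi-square test at significance level of 0.0499", 50 per group are needed. Simulating the unstratified test, (N−1)r² with scores 0 to 4, gives 80.6% (200,000 trials). By normal approximation, se = √((1.2075 + 0.3524)/50) = 0.177, d/se = 2.77 and z = 1.96, so power = Φ(2.77 − 1.96) = 79.2%. The stated 80% therefore reproduces, and it reproduces with the unstratified test.

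**Direction, by formula.** Let ρ be the site share of the event-count variance, with many sites and balance within site.

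- Pooled alpha = 2(1 − Φ(z/√(1−ρ))). At ρ = 0.10 this is 0.039.
- Pooled power = Φ((d/se − z)/√(1−ρ)) = 80.4%.
- Stratified power = Φ(d/(se√(1−ρ)) − z) = 83.2%.

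The gap of 2.8 points is an upper guide, because the formula treats the number of sites as large.

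**Size, by simulation.** The following are assumed, because the available text does not give them: 5 or 10 sites, equal or uneven in size; permuted blocks of four within site; and a normal site effect common to both arms on a latent scale, with the planned marginal distributions kept. There were 100 patients and 20,000 trials per cell, and both tests were run on the same data. The Monte Carlo standard error of the power difference is 0.06 to 0.17 points.

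| Latent site share | Control any-event rate at sites 1 SD below and above average | Pooled alpha | Power change from stratifying (points)* | Ten uneven sites, unpooled |
|---|---|---|---|---|
| 0 | 40–40% | 0.047–0.052 | −0.6 to 0.0 | −1.1 |
| 0.05 | 31–49% | 0.043–0.048 | +0.2 to +0.6 | −0.3 |
| 0.10 | 27–53% | 0.041–0.044 | +0.9 to +1.2 | +0.5 |
| 0.20 | 22–59% | 0.035–0.038 | +2.2 to +2.7 | +1.9 |
| 0.30 | 17–64% | 0.029–0.032 | +3.2 to +4.5 | +3.8 |

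*Equal sites, five uneven sites, or ten uneven sites with sites under 8 patients pooled.

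The stratified test's alpha is 0.045 to 0.051 throughout, and the pooled test's power is 80 to 83% throughout.

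**Robustness.**

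- Two to ten equal sites with exact balance within site, share 0.10: the gain is 0.8 to 1.5 points with 50 per group and 0.7 to 1.4 with 53. Pooled alpha is 0.041 to 0.045.
- A share of 0.10 read on the event-count scale (latent share about 0.145): the gain is 1.1 to 2.2 points with 50 per group.
- Protocol 4.3 does not describe its optimal allocation. Replacing blocks with a within-site biased coin (0.8) at ten equal sites gives −0.6/+0.4/+1.1/+2.7/+4.5 points across the five shares, against −0.6/+0.2/+1.2/+2.7/+4.5 with blocks.

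By normal approximation, the gains at shares 0.10, 0.20 and 0.30 are worth roughly 2–3, 6–8 and 9–14 more patients per 100.

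**The case against.** The strongest reply is that nothing stated in the plan fails. The protocol openly declares an unadjusted analysis, sizes the trial on that test and meets its 80%, and the SAP agrees. The gain rests on a site variance and site layout that the reviewer has to assume, and its sign depends on them: with no site effect, stratifying costs a little. At a share of 0.05 the alpha ranges of the two tests overlap. Replacing the powered primary test in an open trial, with a SAP that already describes randomisation in the past tense, adds an analytic choice where there was none. A pre-specified sensitivity analysis would be the milder step.

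Much of this stands. The point is small and its size is conditional. Two apparent supports are weak. The choice of soft-tissue-reduction technique (protocol 6.2) exists only in the control arm and is not said to vary by site; if site variation affects the control arm only, the gain at 0.10 falls to about 0.3 to 0.5 points. The centre variability that SAP 4.2.5.6 mentions concerns fitting time, not this endpoint. Not testing site between arms is also correct after stratifying on it; it matters here only because it closes the one route to adjustment.

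It does not remove the mismatch. The factor chosen for randomisation enters no planned test of the primary clinical endpoint, using it is cheap, and the added discretion disappears if the pooling rule is fixed in advance without outcome data.

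**Conclusion.** The concern holds as an efficiency point. The pooled test is valid but conservative if outcomes differ by site. At a latent site share of 0.10, common to both arms, it forgoes about 1 point of power. The loss is 2 to 3 points at 0.20, and reaches 4.5 or slightly more only at 0.30, which means large site differences. If there is no site effect, nothing is forgone. Confidence in the size is medium because the site variance, number of sites and site sizes are all assumed. The change is worth making before database lock but is not essential to the trial's validity.

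**What to change.** In protocol 9.4 and 9.5.1.1 and SAP 5.7.1.1, make the confirmatory clinical test the Cochran-Mantel-Haenszel row-mean-score test stratified by site, two-sided at 0.0499. State in the SAP, before database lock and without reference to outcome data, how very small sites are pooled (for example, those with fewer than 8 patients). Keep the unstratified test as a sensitivity analysis and record the change in SAP section 7. The cost test can stay as planned; a site-stratified Wilcoxon (van Elteren) test at 0.0001 is optional, only for consistency with the randomisation.

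The programming cost is one line of SAS plus the pooling rule. The statistical cost arises if site has no effect: 0 to 0.6 power points with equal sites, and 1.1 with ten uneven unpooled sites, which pooling sites under 8 patients cuts to 0.1. The rule is an extra choice in an open trial, which is why it must be fixed in advance.
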